Cover Page for Analysis Plan Document

Official Study Title: What makes people better at retrieving proper names?

NCT05550779

Document Date 9/5/24

Data analysis will be conducted using a two-way ANOVA for each of the TOT measures (TOTs/# familiar trials; TOTs/# known names TOTs/# unsuccessful retrievals) to determine significant main effects, interactions, and simple main effects between the variables. The proposed analysis will determine if there is a) a significant main effect of the manipulation on TOT rate, b) a significant main effect of age on TOT rate, and c) an interaction between mindfulness condition and age group on TOT rate. The two-way ANOVA will be conducted using SPSS (Version 28.0). First, main effects and interactions will be examined. If there is an interaction, simple main effects will be assessed using the Bonferroni adjustment.

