Cover Page for Study Protocol Document

Official Study Title: What makes people better at retrieving proper names?

NCT05550779

Document Date 9/5/24

Research Summary and Participant Information

Research purpose/significance

Provide a brief background and describe the major research question/s of the proposed study in language that can be understood by an individual outside your discipline.

This study tests the relationship between proper name retrieval, age, and a brief mindful breathing exercise intervention. Older adults demonstrate more tip-of-the-tongue (TOT) states compared to younger adults. Mindful breathing exercises are suggested to reduce anxiety and increase attentional functioning; therefore, improve cognitive performance. Overall, I expect that older adults will report more TOT states compared to the younger adults. Additionally, both old and younger adults in the mindful breathing exercise condition (compared to the control condition) should have a decrease in TOT states. This study will test the age effect on TOT rate as well as the magnitude of improvement following a mindful breathing exercise between old and younger adults.

Does this study only involve existing data and no living participants?

No

Methodology

Describe, in narrative format, the research design (descriptions of methods) and list procedures to be used.

The study will test 120 participants, 60 younger adults (ages 18-35) and 60 older adults (ages 60-80). All participants will be treated following the ethical guidelines of the American Psychological Association, and the first step will be providing informed consent to participate. Participants in the mindful breathing exercise condition will listen to a 10-minute guided

meditation presentation. The presentation instructs participants to engage in breathing exercises, and includes music intended to be calming, with binaural beats, which have been found to provide a benefit beyond other mindfulness components. Participants in the control condition will listen to a 10-minute clip of a narration of a story about a scientist's experience on a planet who attempts to communicate with an extraterrestrial being. A mindfulness self-report rating will be asked after the clip.

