Then participants will participate in a name retrieval task in which they will be shown 83 images of celebrities. They will be asked to either retrieve the name the celebrity in the image, say they don't know who the person is, or say the name is on the tip of their tongue. Once all images are shown, the mindfulness self-report rating will be administered once again. After, the participants will be shown the images in which they said they were experiencing a TOT state and asked if the name of the person they were thinking of is the actual name of the person. Then participants will be shown all the images again with the celebrity's name underneath and will be given a familiarity rating of the celebrity in which they rate how familiar they are with the celebrity in the photograph.

For the younger adult participants, after the familiarity rating is completed, the researcher will post in the Zoom chat a Qualtrics link to complete the second part of the study. The researcher will end the Zoom videoconference call and the participants will complete the second part of the study on their own. The second part of the study includes a demographics form, trait mindfulness scale (MAAS), post-study questionnaire (including questions regarding the purpose of the study and meditation habits), and a debriefing of the study.

However, for the older adult participants, after the familiarity rating is completed, the researcher will administer the Mini-Mental State Exam (MMSE; Folstein et al., 1975). Once the MMSE is complete, the older adult participants will receive the Qualtrics link via the Zoom chat, the researcher will end the Zoom videoconference call, and the participants will complete the second part of the study on their own. Data from anyone scoring fewer than 26 out of the maximum score of 30 on the MMSE will be excluded from the analyses with the resulting sample characterized as non-demented elderly.

Do you plan on conducting this research project in person (face to face) with participants?

No

Additional Interaction Information

Is the information recorded in such a manner that subjects can be identified, directly or indirectly or through identifiers linked to the subject?

Yes

Would the disclosure of subjects' responses outside the research place the subjects at risk of criminal or civil liability or be damaging to the subjects' financial standing, employability, insurability, or reputation?

No

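### After a significant interaction the SAP applies Bonferroni to an unnamed family of simple main effects; with two or more effects, Holm's step-down gives the same family-wise error control and a modest gain in power

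*SAP*

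**What the plan says.** The SAP is one paragraph. It plans a two-way ANOVA for each of three TOT measures, "to determine significant main effects, interactions, and simple main effects between the variables". The questions are the main effect of the manipulation, the main effect of age, and "an interaction between mindfulness condition and age group on TOT rate". The follow-up rule, which applies only once an interaction is found, is that "simple main effects will be assessed using the Bonferroni adjustment".

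The SAP does not say which simple effects form the family, how many there are, or what significance level applies, and it gives no reason for choosing Bonferroni.

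The Protocol, under Research purpose/significance, expects a benefit in each age group: "both old and younger adults in the mindful breathing exercise condition (compared to the control condition) should have a decrease in TOT states". It also plans to compare the size of the improvement between the age groups. This makes the condition effect within each age group the natural family for the follow-up.

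**The concern.** With a family of two, Bonferroni tests each within-age condition effect at 0.05/2 = 0.025. Holm tests the smaller p-value at 0.025 and, if that is significant, the larger at 0.05. Both keep the family-wise error at or below 5% whatever the dependence between the tests. Bonferroni therefore gives up rejections without buying any family-wise control.

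The loss falls on the age group with the weaker evidence. That group decides whether a benefit in each age group can be reported when the interaction has led the analyst to the simple effects. Because the family is unnamed, the multiplier could also be 1, 2 or 4, so the same data could lead to different conclusions under the same sentence.

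**Working it through.** **No figure to reproduce.** The documents give no power, significance level, effect size or sample-size derivation.

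**Inputs**
- Sample: 120 participants, 60 younger and 60 older (Protocol, Methodology).
- Allocation to condition: ratio not stated. Assumed 1:1 within each age group, so 30 per cell and 120 − 4 = 116 error degrees of freedom.
- Level: not stated. Assumed two-sided 0.05.
- Family: not stated. Assumed to be two effects, condition within younger and condition within older.
- True effects: not stated. A range in units of a common SD is used.
- Exclusions: the Protocol says "Data from anyone scoring fewer than 26 out of the maximum score of 30 on the MMSE will be excluded from the analyses". It gives no rate, so none is modelled; exclusions would reduce the older cells.

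**Decision rules for two p-values**
- Bonferroni: reject each if p < 0.025.
- Holm: reject the smaller if p < 0.025, then the larger if p < 0.05. As adjusted values: 2 × smaller p, then the greater of that result and the larger p.

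Illustration: p = 0.001 and p = 0.04 become 0.002 and 0.08 under Bonferroni, and 0.002 and 0.04 under Holm.

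**Error control (simulation, no gate).** With both effects null, the family-wise error is 4.9% under either method. With one effect null and the other very large, it is 2.5% under Bonferroni and 5.0% under Holm. Bonferroni then uses half of the allowed error. In no simulated study did Bonferroni reject an effect that Holm did not.

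**Why the interaction gate limits the gain.** The critical t values on 116 degrees of freedom are 1.981 (p = 0.05) and 2.271 (p = 0.025). The interaction statistic is (t1 − t2)/√2, so the gate requires |t1 − t2| ≥ 1.981 × 1.414 = 2.801. Holm's extra room is a second t between 1.981 and 2.271. If both groups benefit, the first t must then be at least 1.981 + 2.801 = 4.78. With standard error √(2/30) = 0.258 SD, that is an observed difference of 4.78 × 0.258 = 1.23 SD.

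**Power behind the gate.** The last three columns give the chance that the interaction and the weaker group's effect are both significant; in the last row they refer to a given group's effect. The gate column can be checked approximately with Φ(difference/0.365 − 1.98), where 0.365 = √(4/30). For example, at 1.4 and 0.5 SD: 0.9/0.365 = 2.46, and Φ(0.48) = 0.68.

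| True effects (SD) | Interaction significant | Bonferroni over two | Holm over two | Gain (points) |
|---|---|---|---|---|
| 0.8 / 0.4 | 19% | 0.4% | 0.9% | about 0.4 |
| 1.0 / 0.5 | 27% | 2.1% | 3.9% | 1.8 |
| 1.2 / 0.5 | 48% | 6.9% | 11.3% | 4.4 |
| 1.4 / 0.5 | 69% | 15% | 23% | about 8 |
| 0.5 / −0.5 | 78% | 36% | 40% | about 4 |

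The first row is 0.43% and about 0.85% before rounding. In the last row one group worsens, so the second effect is not a benefit.

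**The case against.** **Bonferroni is valid and pre-specified.** This stands. A reader might infer that the SAP contains an error; it does not. The point concerns a better choice among valid methods.

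**The loss is conditional.** This also stands. A reader might infer that the stated adjustment certainly lowers power. The SAP does not name the family, so that cannot be said. If comparisons are counted within each age group, there is one per group and the multiplier is 1. Bonferroni then costs nothing, and Holm across the two p-values would add a penalty, because the smaller would be tested at 0.025 instead of 0.05.

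**Large gains need large effects.** This stands. The gain is under 2 points in the same-direction cases with a larger effect of 1.0 SD or less, and the gate decides most of the outcome. Without the gate the gap is wider: at 1.0 and 0.5 SD, both effects are significant in 35.3% of studies under Bonferroni and 46.7% under Holm. That is not the analysis planned. Nor is it fair to set Holm over two effects against Bonferroni over four, since part of that gap comes from dropping two tests.

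**The expectation may not need simple effects.** This stands. If both groups improve similarly, the condition main effect addresses the expectation and the follow-up is not reached.

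**Holm may itself be more than is needed.** This stands in part. For the two condition effects, both nulls being true implies no interaction, and a true interaction allows at most one null. Unadjusted 5% tests behind the gate therefore hold the family-wise error (simulated 3.3% with both null, 5.0% with one). A joint claim that both groups improve would likewise need no adjustment. However, the SAP chose an adjustment and assesses each effect separately. Holm is the like-for-like replacement: it does not rely on the gate, and it extends to a family of four, where the gate argument fails.

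**Simultaneous confidence intervals are less direct under Holm.** This is true, but the SAP plans none.

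**Conclusion.** The point holds as a low-severity efficiency gain, provided the intended family has two or more effects. Holm then keeps the same family-wise guarantee and never rejects less. Behind the interaction gate the gain runs from under half a percentage point to about 8 points over the effects examined, and the upper end needs a very large effect in one age group. The documents offer nothing to show that effects of that size are likely.

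These sizes rest on assumed 1:1 allocation, a two-sided 5% level, a common SD, no exclusions and the assumed effects. The superiority of Holm over Bonferroni within the same family rests on none of them. The guarantee is per TOT measure: neither method, applied within one ANOVA, covers the repetition over three measures.

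A reader might go further and reduce the age effects within condition to description, so as to shorten the family. The documents do not support that. Age is a stated hypothesis in the Protocol and a listed main effect in the SAP, so dropping inference on it would be a trade-off and not a free improvement.

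**What to change.** Replace the SAP's last sentence with one that does the following:
- States the significance level.
- Names the family as the condition effect within each age group, for each TOT measure.
- Applies Holm across those two p-values, computed from the unadjusted output.

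If the effects of age within each condition are also to be tested, keep inference on them, name that family as well, and apply Holm to it. With all four effects in one family, the successive thresholds are 0.05/4, 0.05/3, 0.05/2 and 0.05.

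The cost is a sentence or two in the SAP and a two-line calculation. The small downside is that simultaneous confidence intervals follow less directly from Holm, which matters only if the investigator later wants them.
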